**Figure 4.1.1-1: DFS Primary Definition**

**Table 4.1.1-1: Censoring Scheme used in Primary Definition of DFS**

Situation	Date of Progression or Censoring	Outcome
No baseline disease assessments	Date of randomization	Censored
No on study disease assessments and no death 1)a)	Date of randomization	Censored
No recurrence and no death, and no new anticancer therapy started 1)b) nor new non-urothelial carcinoma primary cancer	Date of last evaluable disease assessment	Censored
Disease at baseline	Date of randomization	DFS event
Any urothelial carcinoma recurrence (i.e. local urothelial tract, local non urothelial tract or distant)	Date of the first recurrence	DFS event

**Table 4.1.1-1: Censoring Scheme used in Primary Definition of DFS**

Situation	Date of Progression or Censoring	Outcome
Death from any cause without recurrence and no new anticancer therapy started 1)b) nor new non-urothelial carcinoma primary cancer	Date of death	DFS event
New anticancer therapy 1)b) received without recurrence reported prior to or on the same day	Date of last evaluable disease assessment prior to or on the same date of initiation of subsequent therapy	Censored
New non-urothelial carcinoma primary cancer without urothelial carcinoma recurrence reported prior to or on the same day	Date of last evaluable disease assessment prior to or on the same date of diagnosis of new non-urothelial carcinoma primary cancer	Censored

a) Disease assessments and death if any, occurring after start of subsequent anti-cancer therapy or after new non-urothelial carcinoma primary cancer are not considered.

b) New anticancer therapy includes systemic therapy, tumor directed radiotherapy and tumor directed surgery (**except TURBT**). As per protocol, the only exception is that a single dose of intravesical chemotherapy instilled immediately after resection of low-risk NMIBC (not considered as a DFS event), is permitted. Therefore **any use of one single dose of chemotherapy given via intravesical route should NOT be considered as subsequent treatment**.

#### 4.1.2 Overall Survival

Overall survival (OS) is key secondary endpoint and defined as the time from randomization to the date of death from any cause. For subjects that are alive, their survival time will be censored at the date of last contact date (or “last known alive date”). OS will be censored at the date of randomization for subjects who were randomized but had no follow-up.

Survival follow-up will be conducted every 3 months after subject’s off-treatment date.

#### 4.1.3 Non-Urothelial Tract Recurrence-Free Survival

Non-Urothelial Tract Recurrence-Free Survival (NUTRFS) is a secondary endpoint of the study and will be programmatically determined based on the disease recurrence date provided by the investigator.

The following NUT recurrences are included in the NUTRFS endpoint:

- Local, Non-Urothelial Tract: Any recurrence in pelvic soft tissue or involving pelvic nodes below the aortic bifurcation
- Distant: Any non-local recurrence

Local urothelial tract recurrence (defined as low-, intermediate- or high-risk NMIBC or invasive urothelial carcinoma in the lower or upper urothelial tract including lesions thought to be a second urothelial carcinoma primary) will **not** be reported as a recurrence event for the NUTRFS endpoint.

[figure not shown]
Subjects who die without a reported recurrence will be considered to have recurred on the date of their death.

NUTRFS rate at time  $T$  (e.g. 6 months, depending on the minimum follow-up) is defined as the probability that a subject has no local non-urothelial tract nor distant recurrence and is alive at time  $T$  following randomization, based on Kaplan-Meier estimate.

As for DFS, the primary definition of NUTRFS (NUTRFS truncated at subsequent therapy **and new non-urothelial carcinoma primary cancer**) is defined as the time between the date of randomization and the date of first documented recurrence (local non-urothelial tract or distant), or death due to any cause, whichever occurs first. The primary definition of NUTRFS accounts for subsequent therapy and new non-urothelial carcinoma primary cancer by censoring at the last evaluable disease assessment on or prior to the date of subsequent therapy/new non-urothelial carcinoma primary cancer.

Detailed censoring rules for the primary definition of NUTRFS are presented in Table 4.1.3-1 and Figure 4.1.3-1.

**Figure 4.1.3-1: NUTRFS Primary Definition**

**Table 4.1.3-1: Censoring Scheme used in Primary Definition of NUTRFS**

Situation	Date of Progression or Censoring	Outcome
No baseline disease assessments	Date of randomization	Censored
No on study disease assessments and no death c)	Date of randomization	Censored
No NUT recurrence and no death, and no new anticancer started d) nor new non-urothelial carcinoma primary cancer	Date of last evaluable disease assessment	Censored
Disease at baseline	Date of randomization	NUTRFS event
NUT recurrence (i.e. local non-urothelial tract recurrence or distant)	Date of the first NUT recurrence	NUTRFS event
Death from any cause without NUT recurrence and no new anticancer started d) nor new non-urothelial carcinoma primary cancer	Date of death	NUTRFS event
New anticancer therapy d) received without NUT recurrence reported prior to or on the same day	Date of last evaluable disease assessment prior to or on the same date of initiation of subsequent therapy	Censored
New non-urothelial carcinoma primary cancer without NUT recurrence reported prior to or on the same day	Date of last evaluable disease assessment prior to or on the same date of diagnosis of new non-urothelial carcinoma primary cancer	Censored

c) Disease assessments and death if any, occurring after start of subsequent anti-cancer therapy or after new non-urothelial carcinoma primary cancer are not considered.

d) New anticancer therapy includes systemic therapy, tumor directed radiotherapy and tumor directed surgery (except TURBT). As per protocol, the only exception is that a single dose of intravesical chemotherapy instilled immediately after resection of low-risk NMIBC (not considered as a DFS event), is permitted. Therefore any use of chemotherapy given via intravesical route (including “BCG”) should NOT be considered as subsequent treatment.

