studies within 4 weeks prior to randomization. Subjects with equivocal nodes less than 15 mm in short axis not considered by the investigator to represent malignant disease may be eligible if discussed and approved by BMS Medical Monitor. All suspect lesions identified during screening radiographic procedures should be discussed with the Medical Monitor prior to randomization.

- i) Imaging studies must include CT of chest and CT or MRI of abdomen, pelvis, and all known sites of resected disease including cystoscopy in subjects with upper GU primaries who still have bladder intact. Brain imaging (MRI except where contraindicated in which CT scan is acceptable) must be completed within 28 days prior to randomization for subjects with clinical suspicion or history of brain/leptomeningeal metastases.
- ii) Subjects who are found to have high-risk NMIBC at the time of screening are not eligible for study entry. Patients with low-risk papillary lesions may enter the study if rendered free of disease at cystoscopy. Subjects with intermediate-risk NMIBC may enter the study if intravesical chemotherapy or BCG is not required. Screening cystoscopy may occur within 60 days of randomization and is encouraged to be done prior to other imaging. Any suspect lesions seen on cystoscopy should be biopsied to rule-out the possibility of high-risk lesions.

Low-risk NMIBC is defined as low-grade lesions or papillary urothelial neoplasms of low malignant potential (PUNLMP; WHO/ISUP 2004 grading system), or TaG1 lesions (WHO 1973 grading system) that are less than 3 cm in diameter.

High-risk NMIBC is defined as any T1 lesion, any lesion containing carcinoma in situ (CIS) either alone or concomitantly with papillary disease (e.g. CIS with Ta/T1 lesions), and any Ta high-grade (TaHG; WHO/ISUP 2004 grading system) or TaG3 (WHO 1973 grading system) lesion.

Intermediate-risk NMIBC is defined as lesions not meeting the criteria of high-risk or low-risk.

- f) Life expectancy \geq 6 months

- h) Prior surgery that required general anesthesia must be completed at least 4 weeks before study drug administration. Surgery requiring local/epidural anesthesia must be completed at least 72 hours before study drug administration. Trans-urethral resection of bladder tumor (TURBT) must be completed 14 days before randomization.

[REDACTED]

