Baseline Tumor Imaging Assessment	X	
CT of chest, and CT or MRI of abdomen, pelvis, upper urinary tract and all known or suspected sites of disease (including cystoscopy in subjects with upper GU primaries who still have bladder intact) within 28 days prior to randomization.
 
MRI brain within 28 days prior to randomization for subjects with clinical suspicion or history of brain/leptomeningeal metastases.

IVRS		
Register Subject in IVRS	X	A call must be made to the IVRS to register subject after signing informed consent.

Table 5.1-2: Treatment Phase (for subjects receiving nivolumab/placebo)

Procedure	During Treatment On Day 1 of Every Cycle (Cycle = 2 weeks)	Notes
Safety Assessments		
Targeted Physical Examination	X	Targeted examination must include at a minimum the following body systems: Cardiovascular Gastrointestinal Pulmonary
Vital Signs	X	Including BP, HR and temperature. Obtain vital signs within 72 hours prior to each dose.
Physical Measurements (including performance status)	X	Weight and ECOG performance status. See Appendix 2 for ECOG Performance Status scale.
Review of Concomitant Medication	X	
Adverse Events Assessment	X	
Laboratory Tests	X	CBC w/differential and platelet count, Chemistry panel including: LDH, AST, ALT, ALP, T. Bili, BUN or serum urea level, creatinine, Ca ⁺⁺ , Mg ⁺⁺ , Na ⁺ , K ⁺ , Cl ⁻ , LDH, albumin, glucose, amylase, lipase. TSH (Reflex to Free T4, Free T3 for abnormal TSH result) to be performed every 6 weeks (every 3 cycles) Urine cytology as clinically indicated (eg, to confirm recurrence in the bladder) On-study local laboratory assessments should be done within 72 hours prior to each dose through Week 23 visit and every alternative dose thereafter. Liver function tests (AST, ALT, ALP, T. Bili) will be analyzed within 72 hours prior to each dose throughout the treatment period.
Pregnancy Test (WOCBP only)	X	Serum or urine pregnancy test to be done within 24 hours prior to first dose, and then every 4 weeks (+/- 1 week) regardless of dosing schedule, or more frequently/at a frequency per local regulations/requirements.

Table 5.1-2: Treatment Phase (for subjects receiving nivolumab/placebo)

Procedure	During Treatment On Day 1 of Every Cycle (Cycle = 2 weeks)	Notes
Efficacy Assessments		

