8.3.2.2 Non-Urothelial Tract Recurrence Free-Survival (NUTRFS)

The secondary endpoint NUTRFS is defined as the time between the date of randomization and the date of first local non urothelial tract or distant recurrence or death (of any cause), whichever occurs first. For subjects who remain alive and local non urothelial tract or distant recurrence-free, NUTRFS will be censored on the date of last evaluable disease assessment.

Detailed censoring rules for the primary definition of NUTRFS are presented in Table 8.3.2.2-1.

Table 8.3.2.2-1: Censoring scheme used in primary definition of NUTRFS

Situation	Date of Progression or Censoring	Outcome
Disease at baseline	Date of randomization	Event
Non-Urothelial Recurrence (ie local non-urothelial recurrence or distant metastasis)	Date of first recurrence	Event
Death from any cause without recurrence	Date of death	Event
No baseline disease assessment	Date of randomization	Censored
No on-study disease assessments and no death	Date of randomization	Censored
No recurrence and no death	Date of last evaluable disease assessment	Censored
New anticancer therapy, tumor directed radiotherapy, or tumor directed surgery received without recurrence reported prior to or on the same day *	Date of last evaluable disease assessment prior to or on the same date of initiation of subsequent therapy	Censored
Second non-urothelial primary cancer reported without recurrence reported prior to or on the same day	Date of last evaluable disease assessment prior to or on the same date of diagnosis of second non-urothelial primary cancer	Censored

*Further details regarding the censoring scheme will be provided in the statistical analysis plan.

Disease assessments as stated in [Section 8.3.1](#).

This endpoint will be analyzed in two different populations (co-primary): Subjects with PD-L1 expression level $\geq 1\%$ and all randomized subjects.

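### The disease-at-baseline row in both NUTRFS tables has no site limit, so baseline disease confined to the urothelial tract would be a day-0 NUTRFS event

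*SAP*

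**What the plan says.** Protocol 8.3.2.2 defines NUTRFS as time from randomization to "the date of first local non urothelial tract or distant recurrence or death (of any cause), whichever occurs first". SAP 4.1.3 uses the same event types and adds an explicit exclusion. The category it describes as "Local urothelial tract recurrence (defined as low-, intermediate- or high-risk NMIBC or invasive urothelial carcinoma in the lower or upper urothelial tract", together with suspected second urothelial primaries, is not to be reported as a recurrence event for this endpoint. The SAP's NUTRFS rate is likewise the probability of being alive without local non-urothelial-tract or distant recurrence.

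The censoring tables then assign outcomes. In SAP Table 4.1.3-1 the post-baseline event row is limited to "NUT recurrence (i.e. local non-urothelial tract recurrence or distant" disease. The row for "Disease at baseline" carries no such limit and gives an event at the date of randomization. Protocol Table 8.3.2.2-1 has a row with the same words, date and outcome.

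The baseline disease assessment covers the urothelial tract. Protocol Table 5.1-1 describes baseline imaging as "including cystoscopy in subjects with upper GU primaries who still have bladder intact) within 28 days prior to randomization".

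**The concern.** NUTRFS exists to set urothelial-tract recurrences aside and measure local non-urothelial-tract failure, distant failure and death. The unrestricted baseline row lets excluded disease back in when it is present at the start. The same bladder lesion is an event if attributed to baseline and a non-event if first found at a later cystoscopy.

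At stake are the level of the NUTRFS curves and the event counts. SAP 7.5.4 classifies each NUTRFS event as recurrence or death, so a day-0 event of this kind would have to appear as a recurrence that SAP 4.1.3 says is not one. The subject's derived NUTRFS time would also be zero, even though Protocol 5.4.1 keeps imaging subjects with urothelial-tract recurrence until a non-urothelial-tract recurrence is documented.

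**Working it through.** The documents give no NUTRFS event count, hazard ratio or power, so there is no planned figure to reproduce. The check is a comparison of rules, followed by a scale calculation.

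**1. The rows side by side**

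| Situation | DFS tables | NUTRFS, SAP Table 4.1.3-1 | NUTRFS, Protocol Table 8.3.2.2-1 |
|---|---|---|---|
| Disease at baseline | Event at randomization, no site limit | Event at randomization, no site limit | Event at randomization, no site limit |
| Post-baseline recurrence | All three recurrence types | NUT recurrence only | NUT recurrence only |
| Rows for no recurrence, death, new therapy, new primary | Site not restricted | Each conditioned on absence of NUT recurrence | Refer to recurrence without a site |

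In DFS the unrestricted baseline row fits, because urothelial-tract recurrence is a DFS event. In the SAP NUTRFS table, all five rows that depend on recurrence status refer to NUT recurrence. The baseline row is the one event row that does not follow the endpoint's site rule.

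**2. One subject under the rules**

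Take an upper-tract subject with an intact bladder who was randomized and is later found to have had high-risk NMIBC at baseline.

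- Eligibility: "Subjects who are found to have high-risk NMIBC at the time of screening are not eligible for study entry". The subject is a deviation but stays in the all-randomized population.
- Baseline row: NUTRFS event, time 0.
- Same lesion first seen at the Week 12 cystoscopy: not a NUTRFS event under SAP 4.1.3. NUTRFS time runs on until NUT recurrence, death or censoring.

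**3. Who could be affected**

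- High-risk NMIBC: only by deviation, as above.
- Low-risk lesions: "Patients with low-risk papillary lesions may enter the study if rendered free of disease at cystoscopy". A cleared lesion should not be disease at baseline.
- Intermediate-risk NMIBC: "Subjects with intermediate-risk NMIBC may enter the study if intravesical chemotherapy or BCG is not required". Whether an admitted lesion counts as disease at baseline is not stated.
- SAP 7.2.2 lists presence of disease at baseline among the entrance deviations, so the plan foresees such subjects among those randomized. It gives no site there either.

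An intact bladder is mainly an upper-tract matter, and upper-tract enrolment is capped at about 20% × 700 = 140. No document gives the share of these subjects with urothelial-tract disease at baseline.

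**4. Size per affected subject**

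Inputs: about 700 subjects randomized 1:1 and about 42% with PD-L1 ≥1% (SAP section 5).

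- All randomized: 700/2 = 350 per arm.
- PD-L1 ≥1%: 0.42 × 700 = 294. Assuming an even split, 294/2 = 147 per arm.
- With k events at time 0 among n subjects at risk, the Kaplan-Meier estimate starts at 1 − k/n, a drop of 100 × k/n points.

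| k in one arm (assumed, for scale only) | All randomized, n = 350 | PD-L1 ≥1%, n = 147 |
|---|---|---|
| 0 | 0 | 0 |
| 1 | 0.29 points | 0.68 points |
| 5 | 1.43 points | 3.40 points |

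Without censoring, each subject's share of the drop lasts until that subject would have had a true NUTRFS event.

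**The case against.** The strongest reply rests on how the SAP uses the term. Outside the censoring tables, SAP 7.2.2 treats disease at baseline as a deviation from eligibility. Read that way, a subject with intermediate-risk NMIBC whom the inclusion criteria expressly admit is not a deviation and does not trigger the row. A reader might infer that eligible intermediate-risk subjects become day-0 NUTRFS failures. The documents do not establish this: the term is undefined in the available text, and the one other use points the opposite way. Nor do they rule it out.

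A reader might also want to turn the cap of about 140 upper-tract subjects into a number of false events. That needs a rate of baseline urothelial-tract disease, which the documents do not supply. Zero is possible.

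Other points on this side also have weight:

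- Eligibility closes most routes. High-risk NMIBC is excluded, low-risk lesions must be cleared, and suspect cystoscopic lesions should be biopsied.
- SAP 4.1.3 refers to Figure 4.1.3-1 as well as the table. That figure is not shown and could carry a site limit.
- Imaging continues after urothelial-tract recurrence, so data collection need not stop. It is the derived time that stops at zero.
- In a blinded randomized trial there is no reason to expect such cases to favour one arm.

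These arguments limit the reach and size of the problem. They do not remove it. The deviation reading itself confirms that the row is meant for randomized subjects with disease at baseline, and nothing in the available text tells a programmer to set aside those whose disease is only in the urothelial tract.

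**Conclusion.** The point holds as an internal inconsistency in a secondary endpoint. Applied as written, the baseline row in both NUTRFS tables produces an event that SAP 4.1.3 excludes when the disease is confined to the urothelial tract. This is clear for subjects randomized despite not meeting the disease-free criterion. For eligible intermediate-risk NMIBC it remains unresolved.

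The effect is probably small. It is the per-subject drop worked out above, multiplied by an unknown and possibly zero count. The PD-L1 figure assumes an even split between arms. The main effect is on the level of the curves and the event tally, not on the comparison between arms. Protocol 8.4.2.2 and SAP 7.5.4 provide no formal NUTRFS comparison, although SAP 7.5.4 still reports a log-rank p-value. DFS, OS and type I error are unaffected. This is a low-priority correction.

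**What to change.** In SAP Table 4.1.3-1 and Protocol Table 8.3.2.2-1, change the row to: *Non-urothelial-tract (local non-urothelial-tract or distant) disease at baseline*, keeping the date of randomization and the event outcome. Add one sentence stating that disease confined to the urothelial tract at baseline is not a NUTRFS event and that NUTRFS time continues under the remaining rows. Check that SAP Figure 4.1.3-1 agrees. The DFS tables need no change for this point.

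With the row limited in this way, NUTRFS no longer depends on whether eligible intermediate-risk NMIBC counts as disease at baseline. The cost is one table row and one sentence in each document, plus a site condition in the NUTRFS derivation. No alpha, power or sample-size figure changes.

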#### **4.1.4 Disease-Specific Survival**

Disease-Specific survival (DSS) is a secondary endpoint and defined as the time from randomization to the date of death due to disease (urothelial cancer). For subjects that are alive, their survival time will be censored at the date of last contact date (or “last known alive date”). DSS will be censored at the date of randomization for subjects who were randomized but had no follow-up.

Death not due to disease will be considered as a competing risk. Consequently, for subjects who died due to other cause than urothelial cancer, DSS in the analysis of cause-specific hazard analysis will be censored on the date of death.

DSS will be followed continuously as part of OS follow-up.

[figure not shown]

## **5 SAMPLE SIZE AND POWER**

The sample size for this study is based on a comparison of the DFS distribution between subjects randomized to receive nivolumab and subjects randomized to receive placebo. There will be two co-primary comparisons: in subjects with PD-L1 expression  $\geq 1\%$  and in all randomized subjects with an alpha allocation of 2.5% (two-sided) each.

The prevalence of subjects with PD-L1 expression  $\geq 1\%$  is expected to be around 42%. In time-to-events trials, the number of events and power may typically be calculated assuming an exponential distribution in each treatment arm. However for DFS, a meaningful number of long-term disease-free survivors may be observed. As a consequence, the DFS curves may not follow an exponential decay and a flattening of the curves may be observed toward the end of the tail. Consequently, an exponential cure rate distribution was used to calculate the sample size.

The exponential cure rate distribution can be described with following formula:

$$S(t) = p + (1 - p) * \{e^{-\alpha t}\},$$

where  $p$  is the cure rate and  $\alpha$  is the parameter of the exponential distribution for the non-cured population.

Based on historical data, median DFS distribution in the control arm is assumed to be 12 months with a 5 year DFS rate of 32% used as the cure rate (i.e.,  $p=0.32$  and  $\alpha=0.11$ ). It is also assumed that DFS distribution in control arm does not depend on the PD-L1 expression level. Cure rates in subjects with PD-L1 expression  $\geq 1\%$  and in the all randomized population for the experimental arm are targeted to be 54% and 47% respectively while non cured population is assumed to follow same distribution as in the control arm. It is assumed that the effect of nivolumab vs. placebo will be delayed. A study of nivolumab vs. ipilimumab in metastatic melanoma (CheckMate 238) suggested a 3-month delayed effect for nivolumab, therefore the model used for the experimental arm also assumes a 3-month delayed effect in subjects with PD-L1 expression  $\geq 1\%$  and in the all randomized population for the experimental arm.

Approximately 700 subjects will be randomized in 1:1 ratio to nivolumab arm and control arm respectively.

- Approximately 410 DFS events in all randomized subjects will provide around 87% power to detect an average HR of 0.72 with an overall type I error of 2.5% (two-sided)
- Approximately 162 DFS events in subjects with PD-L1 expression  $\geq 1\%$  (~294 subjects) will provide around 80% power to detect an average HR of 0.61 with an overall type I error of 2.5% (two-sided).

The target average hazard ratios were obtained via simulation using above modeling.

It is expected that the required number of events in each population will be reached when all subjects will have at least a minimum of 17 months of follow-up.

An interim DFS analysis (in all randomized subjects and in subjects with PD-L1 expression  $\geq 1\%$ ) will also be performed when 85% of DFS events in all randomized subjects (i.e., 348 DFS events) and in subjects with PD-L1 expression  $\geq 1\%$  (i.e., 137 DFS events) will be observed. The alpha level for DFS will be adjusted for the planned interim analysis using Lan-DeMets alpha spending function with the O'Brien-Fleming type of boundary in East v6.

Assuming an average accrual rate of 16 subjects per month, the accrual will take approximately 43 months. The total duration of the study from start of randomization to final analysis of DFS is expected to be 60 months (43 months of accrual + 17 months of follow-up).

DFS analyses in all randomized population and in subjects with PD-L1 expression  $\geq 1\%$  are projected to occur 45 months after start of the study for the interim analyses and 60 months (43 months of accrual + 17 months of follow-up) for the final analyses (Table 5-1 and Table 5-2).

It is expected that interim DFS analysis (defined as analysis timepoint T1) in each population will occur at the same time. However, because the DFS event rate pattern may be different between all randomized population and subjects with PD-L1 expression  $\geq 1\%$ , the interim DFS analysis of each population might also occur separately.

The final analysis of DFS in each population will be performed at the same time when 410 and 162 events of DFS are observed in all randomized subjects and in subjects with PD-L1 expression  $\geq 1\%$ , respectively (defined as analysis timepoint T2).

